Physical activity in the past week will be measured using three screening questions developed for the Swedish national board of health and welfare.

1. Self-reported physical activity in the past week regarding moderate to intensive exercise (minutes)
2. Other physical activity beside exercise (minutes)
3. Sitting time (minutes during a regular day)
 - Time Frame: collected at baseline, 24 -72 hours prior to the initial physiotherapy consultation, 24 hours post initial physiotherapy consultation and at three months post-baseline.
 - Calculation to derive outcome:
 - Within and between group mean change in the scores over time from baseline to follow-up three months post-baseline (all time points). Scores on question regarding “Moderate to intensive exercise” and “Other physical activity beside exercise” will also be converted to activity minutes per week < 150min/w or \geq 150min/w.

-Global rating of change

Global rating of change will be measured using a single item Global Rating of Change Scale (GRoCs) scored on an 11-point scale from minus five to plus five, anchored by the terms very much worse (minus five), unchanged (zero) and completely recovered (plus five). The score is based on the period from when the patient first contacted the physiotherapy department to initiate triage until the data collection points for the GRoCs.

- Time Frame: collected at 24 -72 hours prior to the initial physiotherapy consultation, 24 hours post initial physiotherapy consultation and at three months post-baseline.
- Calculation to derive outcome:
 - The score will be dichotomized into improved (1-5) and unchanged/worse (-5-0).

-Analgesic medication use

Self-reported analgesic medication use (type and consumption) for the presenting MSKP complaint will be established via two questions. The first question establishes self-reported consumption of analgesics with the answer alternatives: Yes, on a regular basis; Yes, sometimes; or No. The second question establishes the type of analgesics taken for MSKP and is ranked according to the analgesics ladder recommendations from the Östergötland health care region pharmaceutical committee (2024) (1. Paracetamol, 2. NSAID, 3. Opioids/gabapentinoids/Tricyclic antidepressants/Serotonin-norepinephrine reuptake inhibitors).

- Time Frame: collected at baseline, 24 -72 hours prior to the initial physiotherapy consultation, 24 hours post initial physiotherapy consultation and at three months post-baseline.

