minimum sufficient adjustment set includes age, sex, BMI, pain duration, number of pain sites, comorbidity, employment, level of education, days to initial physiotherapy consultation, analgesic medication consumption and previous health care interventions. The analyses will also be adjusted for physiotherapist characteristics: age, sex, clinical experience and educational level. Baseline measures of the mediator and outcome will also be included in the models.

Statistical analysis

Single causal mediation analysis will be used to analyse the PainSMART's indirect effects on pain intensity (NRS) and pain self-efficacy (PSEQ-10) through improvement in MSKP illness perceptions (BIPQ) and reassurance of the benign nature of MSKP (NRS). The direct acyclic graph model in Figure 2 summarizes these causal inferences.

For each mediator on each outcome the following will be estimated:

1. The effect for the intervention–mediator relationship, the intervention-outcome relationship and the mediator-outcome relationship.
2. The indirect and direct effects of the intervention on the outcome considering the mediator (single mediated effect).
3. The proportion mediated which is the fraction of the intervention-outcome relationship that is explained by the indirect effect.

Regression-based inference approach will be used for causal mediation analysis. The analysis allows the total effect to be broken down into separate effects (paths) using regression coefficients. The mediation models will be estimated using path-analyses within the framework of Structural Equation Modelling, where all the variables are manifest (i.e., measurable). The mediator models will be constructed with the treatment allocation (binary coded variable 0 = control group, 1 = intervention group) as the independent variable. For each mediator model the intervention-mediator effect (a-path), the mediator-outcome effect (b-path), the average causal mediation effect (indirect effect, ab-product), the average direct effect (c'), and the average total effect (c) will be estimated. The indirect effect is the average intervention effect through the mediator; the direct effect is the average intervention effect that works through all other mechanisms, excluding the selected mediator; and the total effect is the average effect of the intervention on the outcome (MacKinnon, 2012). Effects will be reported with 95% CI.

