The secondary objective is to explore if pain self-efficacy mediates the effect of the PainSMART-strategy on health outcomes of interest. Based on an integration of the CSM and concept of self-efficacy, the effect of MSKP illness perceptions and level of reassurance of the benign nature of MSKP on pain self-efficacy act as a first step in the causal pathway of the PainSMART-strategy's effect on health outcomes. As a second step in the causal pathway in the integrated model, the effect in pain self-efficacy is hypothesized to mediate the effects

on health outcomes. The theoretical rationale underlying the hypothesised mediators in the PainSMART-strategy are explained in full in the trial protocol.

Outcomes and data collection

Outcomes (dependent variables) are health outcomes hypothesised to be improved by the PainSMART-strategy (pain intensity, levels of physical activity, Global rating of change, number of healthcare visits, analgesic medication use, sick leave days). The hypothesised mediator is pain self-efficacy measured with the PSEQ-10. Data collection of the outcomes and mediator is the same as for the primary mediation analyses, see “Mediation analyses”.

Models and causal model assumptions

The potential mediating effects of change in pain self-efficacy at time point 2 (after exposure to the film) and at time point 3 (after exposure to the whole PainSMART-strategy) on the outcome will be analysed. The causal model assumptions are the same as for the primary mediation analyses, see “Mediation analyses”.

Statistical analysis

Causal mediation analysis will be used to analyse the PainSMART’s indirect effects on health outcomes through improvement in pain self-efficacy (PSEQ-10). The mediation models will be estimated using path-analyses within the framework of Structural Equation Modelling.

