The relationships that will be estimated for each mediator on each outcome are described in the primary mediation analyses, see “Mediation analyses”. The mediator models will be adjusted for the baseline score in the dependent variable (outcome), the mediator as well as the potential pre-treatment confounders. The interaction term between the intervention allocation and the mediator will be analysed to examine its impact on the indirect effects. The interaction term will be adjusted for in the outcome model if indicated. Missing data will be handled using full information maximum likelihood in the mediation analyses, if other methods are not indicated. The effects will be reported with 95% CI.

Predictors and sub-groups

-Baseline predictive factors

All baseline factors will be explored as potential predictors for health outcomes at time point 4 for the PainSMART intervention group cohort and also for the entire cohort. Regression based statistics will be used. Prediction models will be constructed exploring predictive performance. Internal and external validation of the models will be explored.

-Moderator analyses

Moderator analyses are planned based on the ÖMPSQ risk group categories. The two sub-groups are defined as high risk (score >50) and low risk (score ≤ 50) for persisting disability and work absence. The dependent variable is the intervention’s effect on health outcomes at time points 3 and 4.

Missing data

Proportion of missing and available data will be investigated through completion rate for each outcome measure and at all data collection time points. The proportion and patterns of missing data in outcomes will be assessed if missing data is $>5\%$. Comparison of characteristics and baseline score on PROMs between participants with and without missing data at one or several data collection time points or according to specific missing data patterns will be analysed to interpret the potential impact of missing data on generalizability.

Imputation will be conducted and handled under the missing at random assumption. In the event of substantial missing data, an evaluation of the mechanisms for missing data will be conducted (Enders, 2011). Multiple Imputation or Restricted Maximum Likelihood estimation will be used assuming that missing data is conditional on variables included in the model. Other imputation methods may be used if necessary.

[Statistical software](#)

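### Exploratory mediation: linear path rules are carried over to binary and categorical outcomes, where ab/c is not the proportion mediated, and a baseline outcome score is required where none exists

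*SAP*

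**What the plan says.** The SAP, Exploratory mediation analysis, names pain self-efficacy (PSEQ-10) as mediator and lists the outcomes as "pain intensity, levels of physical activity, Global rating of change, number of healthcare visits, analgesic medication use, sick leave days". Its Statistical analysis paragraph gives no separate effect definitions: "The relationships that will be estimated for each mediator on each outcome are described in the primary mediation analyses". It also adjusts every model for the baseline score of the dependent variable, with no exception, and adds an intervention-by-mediator interaction to the outcome model if indicated.

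The section referred to (SAP, Mediation analysis, Statistical analysis) was written for the pain NRS and the PSEQ-10. It states that "the average causal mediation effect (indirect effect, ab-product), the average direct effect (c'), and the average total effect (c) will be estimated", on the premise that "The analysis allows the total effect to be broken down into separate effects (paths) using regression coefficients". It then asks for "The proportion mediated which is the fraction of the intervention-outcome relationship that is explained by the indirect effect". The caption to SAP Figure 2 makes c the total effect from a model that leaves the mediator out.

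Elsewhere the SAP treats several of the listed outcomes as non-continuous:

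- **Global rating of change:** dichotomised into improved against unchanged or worse (Outcome definitions).
- **Global rating and analgesic consumption:** listed as dichotomous, with between-group results as odds ratios (Secondary outcome analysis, Categorical variables).
- **Type of analgesic:** multinomial, by generalised logit models (same section).

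The rating is first "collected at 24 -72 hours prior to the initial physiotherapy consultation", then after the consultation and at three months. Register visits and sick-leave days are collected for the period from baseline to three months.

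**The concern.** The decomposition rests on the identity c = c' + ab. That identity holds for a continuous outcome with linear models. It does not hold in general when the outcome model is logistic: leaving the mediator out of the model changes the scale of the treatment coefficient as well as its content. The ratio ab/c then combines a numerator from one model with a denominator from another on a different scale, and no sample size corrects it.

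The baseline rule raises a separate problem. A rating of change since first contact cannot have a baseline value, and a count that starts at baseline has no earlier value in the data to be collected.

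At stake are the reported total, direct and mediated shares behind exploratory research question 4, for the outcomes that are not continuous.

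**Working it through.** The plan states no figure on this point, so there is none to reproduce. The documents give no path sizes; all values of a, b and c' below are assumptions, shown over a range.

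**Model.** Mediator M = aA + e, with e standard normal and A the arm (0 or 1). Binary outcome: logit P(Y=1) = i + c'A + bM. The model without the mediator gives, in large samples,

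c = logit E[expit(i + c' + b(a + e))] − logit E[expit(i + be)].

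The expectations were evaluated by numerical quadrature. The counterfactual (natural) indirect share on the risk scale is [P(1, M under intervention) − P(1, M under control)] / [P(1, M under intervention) − P(0, M under control)].

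**Reference case, continuous outcome.** With a = 0.5, b = 0.5, c' = 0.3: c' + ab = 0.30 + 0.25 = 0.55. The fitted c (n = 400,000 simulated) is also 0.550, so the paths add up.

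**One binary setting in full.** a = 0.4, b = 1.0, c' = 0.2, i = 0. P(control) = 0.500, P(intervention) = 0.6218, P(intervention with the control-arm mediator) = 0.5412.

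- c = ln(0.6218/0.3782) − 0 = 0.497, but c' + ab = 0.2 + 0.4 = 0.600.
- ab/c = 0.4/0.497 = 0.80.
- (c − c')/c = 0.297/0.497 = 0.60.
- Risk-scale share = (0.6218 − 0.5412)/(0.6218 − 0.5000) = 0.66.
- ab/(ab + c') from the one outcome model = 0.4/0.6 = 0.67.

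**Range, a = 0.4.** The two values in a cell are for i = −2 (control-arm rate 13% to 19%) and i = 0 (50%).

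| c' | b | c | c' + ab | ab/c | (c − c')/c | Natural share, risk scale | ab/(ab + c') |
|---|---|---|---|---|---|---|---|
| 0 | 0.5 | 0.194, 0.189 | 0.200 | 1.03, 1.06 | 1.00 | 1.00 | 1.00 |
| 0 | 1.0 | 0.349, 0.331 | 0.400 | 1.15, 1.21 | 1.00 | 1.00 | 1.00 |
| 0 | 1.5 | 0.447, 0.425 | 0.600 | 1.34, 1.41 | 1.00 | 1.00 | 1.00 |
| 0.2 | 0.5 | 0.387, 0.378 | 0.400 | 0.52, 0.53 | 0.48, 0.47 | 0.533, 0.496 | 0.50 |
| 0.2 | 1.0 | 0.521, 0.497 | 0.600 | 0.77, 0.80 | 0.62, 0.60 | 0.699, 0.661 | 0.67 |
| 0.2 | 1.5 | 0.593, 0.568 | 0.800 | 1.01, 1.06 | 0.66, 0.65 | 0.775, 0.745 | 0.75 |

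Over a wider set (c' = 0.3, a = 0.25 to 0.5, b = 0.5 to 1.5), c' + ab exceeds c by 1.5% to 20% at a control rate of 5%, 4.4% to 36% at 20%, and 5.8% to 41% at 50%.

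**Multinomial logit** (four categories, a = 0.5, n = 400,000 simulated). c' + ab = 0.453, 0.812, 1.050 against c = 0.384, 0.672, 0.847. The paths do not add up, and each category has its own b.

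**Counts, log link, no interaction.** a = 0.5, b = −0.5, c' = −0.1: c' + ab = −0.350 and c = −0.350, so the paths add up. With an interaction of 0.2 (a = 0.5, b = −1.0, c' = −0.1), c = −0.680 against c' + ab = −0.600. Scale still matters: in the first setting the share is 0.25/0.35 = 0.71 on the log scale and 0.374/0.552 = 0.68 on the mean-difference scale.

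**Baseline scores, outcome by outcome.**

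- Pain intensity, physical activity and analgesic use: collected at baseline.
- Global rating of change: time points 2, 3 and 4 only.
- Register visits and sick-leave days: counted from baseline to three months. The only earlier information is self-reported at baseline: healthcare visits in the previous three months, and current sick leave yes or no (Protocol, Secondary outcome measures).

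**The case against.** The strongest reply is that the exploratory section names no link function. A linear model for a binary outcome, or a total defined as ab + c' within one model, would add up by construction, so the gap would be missing detail and not a wrong rule. In part this stands: the logit link is inferred from the SAP's analysis of the same outcomes under Categorical variables. But neither alternative is named, and the Figure 2 caption defines c without the mediator. Calling the method causal mediation does not help either, because the SAP equates the average causal mediation effect with the ab-product.

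Several stronger readings are tempting and should not be drawn.

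- **That counts fail too.** They add up under a log or linear link without interaction, and the SAP's own analysis of register visits and sick-leave days works with group means. For counts the open matters are the unstated model and scale, the possible interaction term, and the missing baseline.
- **That proportions above 100% are to be expected.** With a direct effect of 0.2, ab/c passes 1 only at b = 1.5. With no direct effect it always does, but by just 0.03 to 0.06 at b = 0.5. Nothing in the documents says that b is large.
- **That the ab-product itself is wrong, or that a risk difference is required.** ab/(ab + c') from the single outcome model is 0.67 at b = 1.0 and c' = 0.2, close to the natural share on the log-odds scale (0.66 to 0.67) and on the risk scale (0.66 to 0.70). The error comes from dividing by a separately fitted c.
- **That question 4 cannot be answered.** Whether self-efficacy is a potential mediator can be judged from the indirect effect and its interval, without a proportion.

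One might also point to the SAP's Healthcare register outcome analyses, which mention baseline means for the register outcomes. The outcome definitions give no period before baseline from which to form them.

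**Conclusion.** The point holds, within limits. Two stated rules do not work as written for part of the exploratory list.

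1. For the dichotomised global rating and for analgesic use, analysed on the logit scale, the proportion mediated as ab/c is biased upward on that scale in large samples. At b = 1.0 the excess is roughly 0.1 to 0.2. It is about 0.02 to 0.06 at b = 0.5, and the non-additivity is also small for rare outcomes with a weak b-path. These sizes rest on assumed paths, a normally distributed mediator and no interaction.
2. The baseline-score adjustment cannot be carried out for the global rating or for the register counts.

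Pain intensity and activity minutes are continuous and escape the first problem; the version of physical activity cut at 150 minutes per week would not, if it is the one used. The documents do not support extending the point to the primary analysis or to the eight confirmatory mediation models, whose outcomes are continuous. It is a minor point, worth settling before analysis because it costs little.

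**What to change.** Amend the Statistical analysis paragraph of the SAP's Exploratory mediation analysis as follows.

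- For each non-continuous outcome, state the link and the effect scale (risk difference or odds ratio for binary and categorical outcomes; ratio or mean difference for counts).
- Report counterfactual natural direct and indirect effects on that scale. Take the total effect and the proportion mediated from the same fitted model, not from ab over a separately fitted c. State how an interaction term, if kept, enters these effects.
- Adjust for the baseline value of the outcome only where it is collected. For the global rating, add baseline pain intensity. For the register counts, use the self-reported baseline healthcare-visit and sick-leave items. Previous healthcare interventions are already in the adjustment set, and baseline PSEQ-10 already enters as the mediator's baseline; baseline pain and current sick leave are not named there.

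The cost is SAP wording and slightly more analysis work. No new data are needed, and the sample size and primary analysis do not change.

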The short form of the Örebro musculoskeletal pain screening questionnaire (ÖMPSQ) will be collected at baseline (Linton et al., 2011). The ÖMPSQ is a ten-item questionnaire which assesses five constructs; self-perceived function, pain experience, distress, fear-avoidance beliefs and return to work expectancy (Linton et al., 2011). The ÖMPSQ was developed in a

primary care setting and the questionnaire is scored from 0-100 where a higher score indicates higher risk for future work-related disability (Linton et al., 2011). However, the predictive ability of the ÖMPSQ remains uncertain (Silva et al., 2022). The ÖMPSQ is included in this study to evaluate whether a certain sub-group of patients, based on ÖMPSQ scores, respond to the PainSMART-strategy.

Patient and Physiotherapist Reported Experience Measures (PREMs)

In this study PREMs will be collected after the film for the intervention group only, and 24 hours after the initial physiotherapy consultation for both groups. The questions posed to the physiotherapists regarding their perception of the participating patients' degree of preparation for their initial consultations will be collected following completion of the initial consultations in the RCT.

- Evaluation of the intervention group's experiences of the film

The intervention group will rate the clarity of the key-messages in the film (Table 2) on a numerical rating scale of zero to ten anchored by the terms, not at all clear and completely clear. These questions are obligatory to increase adherence, reinforce the film's key-messages and to assess whether the patients receiving the intervention pick up on the film's intended messages.

- Evaluation of MSKP-related shared understanding, communication, participation, involvement and emotional support at the initial physiotherapy consultation

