Physiotherapist consent and background data will be collected via Webropol questionnaires prior to the start of patient recruitment. English language copies of the data collection questionnaires (patient and physiotherapist PROMs and PREMs) are available from the corresponding author on request. The physiotherapists' evaluations of the initial consultation will be sent to the study coordinators via the messenger function of the electronic journal system within RÖ and RJL. All physiotherapists who have conducted at least one initial PainSMART consultation in the RCT will be sent a follow up Webropol questionnaire containing four questions. These four questions ask the physiotherapists to self-report their adherence to the study protocol for each group and rate their experiences of the participating patients' degree of preparedness for the initial consultations. For physiotherapists who consent to continue participation in the RCT for the qualitative phase, additional data will be collected via Dictaphone audio recordings of the initial physiotherapy consultation. The audio recordings will then be uploaded to Linköping University's secure NextCloud service.

Sample size

The sample size calculation for this study is based on its primary hypotheses. The calculations are based on the MCID of $2 \pm SD/4$ for the NRS for pain intensity and a minimal detectable change of $11.52 \pm SD/23.20$ for the PSEQ-10 (Dube et al., 2021; Olsen et al., 2017; Olsen et al., 2018; Ostelo et al., 2008). Sample size calculations were computed for both primary outcomes (NRS and PSEQ-10) using a Cohen's f effect size of = 0.25 (i.e. small-moderate) and a one-sided p-value of $p=0.05$ plus a statistical strength of 0.8 (=Power 80%). The largest sample size calculated was for analysis of the NRS ($n = 102$ per group) and this was adopted as the sample size for this study. To enable mediation and sub-group analyses two subgroups are required. This gives a total sample size of 408 patients. A drop-out rate of approximately 30% was factored into the randomisation sequence giving a total sample of 600 patients.

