- Previous healthcare interventions for the actual presenting complaint in the last three months
- Previous healthcare interventions for other MSKP sites in the last three months

- Analgesic medication use (type and consumption)
- Number of comorbidities
- Risk for future work-related disability – low or high risk according to score on Örebro musculoskeletal pain screening questionnaire (ÖMPSQ), where >50 is classified as high-risk.
- Average waiting time to initial physiotherapy consultation

Baseline PROM scores

- Pain intensity with numerical rating scales (NRS).
 - o Worst pain in the last 24 hours (0-10).
 - o Best pain in the last 24 hours (0-10).
 - o Average pain in the last 24 hours (0-10).
- Pain self-efficacy - Pain self-efficacy questionnaire (PSEQ-10; max score 60).
- Traditional pain coping - Brief Pain Coping Inventory (BPCI-2) traditional pain coping subscale (max score 56).
- Psychological flexibility in pain - BPCI-2 psychological flexibility subscale (max score 49).
- MSKP illness perceptions - Brief Illness Perception Questionnaire (BIPQ; max score 80).
- Level of concern as to the potential likelihood of MSKP being caused by a serious pathology - Single question rated on a NRS (0-10).
- Self-reported physical activity in the past week based on three questions
 - o Moderate to intensive exercise (minutes)
 - o Other physical activity beside exercise (minutes)
 - o Sitting time (minutes during a regular day)

Physiotherapists will be described with respect to age, sex, level of education and number of years working as a physiotherapist. Data will be presented for the whole cohort of physiotherapists and separately for the physiotherapists providing treatment in the two randomised groups.

Normally distributed continuous data will be summarised by mean, standard deviations (SD). For non-normally distributed continuous data, median and lower, upper quartile range, will be provided unless otherwise stated. Categorical data will be summarised by number and percentages. Tests of statistical significance will be undertaken for screening of imbalance between groups in baseline characteristics.

Analysis

Time frame for data collection

Primary and secondary patient reported outcome measures (PROMs) will be collected at four time points:

1. Baseline: the same day as initial triage.
2. 24 -72 hours prior to the initial physiotherapy consultation.
3. 24 hours post the initial physiotherapy consultation (primary time point one).

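### The exploratory ÖMPSQ moderator analysis rests only on a split at 50 and names no interaction term; an arm by continuous-score interaction should be added as the main test

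*SAP*

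**What the plan says.** In the SAP, under Secondary exploratory analysis, Predictors and sub-groups, "Moderator analyses are planned based on the ÖMPSQ risk group categories". The two categories are a score above 50 (high risk) and a score of 50 or below (low risk). The SAP's baseline-characteristics list uses the same definition: "where >50 is classified as high-risk". The dependent variable is described as the intervention's "effect on health outcomes at time points 3 and 4", that is, 24 hours after the initial consultation and three months after baseline. No model, interaction term or estimate is given.

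The Protocol (Outcomes, Screening tool) describes the instrument as a score: "the questionnaire is scored from 0-100 where a higher score indicates higher risk for future work-related disability". It says the scale was included to "evaluate whether a certain sub-group of patients, based on ÖMPSQ scores, respond to the PainSMART-strategy".

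The only other related plan is the Baseline predictive factors paragraph in the same SAP section. It explores all baseline factors as predictors of outcome at three months, in the intervention cohort and in the entire cohort. It describes no interaction with arm, so it is prognostic modelling and does not test moderation.

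**The concern.** Two things are missing from a question the Protocol gives as the reason for collecting the scale.

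- **The score is used only as two categories.** Patients scoring 51 and 95 are treated alike, and patients scoring 49 and 51 are treated as different in kind. If the effect changes gradually with the score, the split discards information from a test that has little to spare.
- **The test is not defined.** The intervention's effect is not something any single patient has as a measured value, so it cannot be a dependent variable in the ordinary sense. The intent is presumably effect modification. But since no interaction is named, a significant effect in one risk group and a non-significant effect in the other could be reported as moderation. That pattern is not evidence that the two effects differ.

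At stake is how reliable and readable an exploratory subgroup result will be. The trial's main conclusions are not affected.

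**Working it through.** **Inputs from the documents.** Score range 0-100 and cut at above 50 versus 50 or below (Protocol, Screening tool; SAP, Predictors and sub-groups). Allocation 1:1. Total of 408 patients (Protocol, Sample size), which reproduces as 102 per group × 2 arms × 2 subgroups = 408. Only the total of 408 is used below.

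**Inputs that are assumptions.** Neither document gives the ÖMPSQ mean, SD, shape or expected share above 50, nor a size of interaction. I assume a roughly normal score and linear moderation, high-risk shares of 50%, 30% and 20%, and an interaction of 0.20 (also 0.25) outcome SD per SD of ÖMPSQ.

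**Step 1: information kept by the split.** Under linear moderation, the efficiency of arm × category relative to arm × score is the squared correlation between the score and its indicator. For a normal score with upper share p cut at z, this is φ(z)² / [p(1 − p)].

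- p = 0.50: 0.3989² / 0.25 = 0.637
- p = 0.30: 0.3477² / 0.21 = 0.576
- p = 0.20: 0.2800² / 0.16 = 0.490

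Multiplied by 408, these are worth about 260, 235 and 200 patients analysed on the continuous score.

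**Step 2: power.** With a standardised moderator and 1:1 arms, the standard error of the interaction is 2/√408 = 0.099 residual SD. Power at two-sided 5% is Φ(τ/0.099 × √efficiency − 1.96). For τ = 0.20, τ/0.099 = 2.02; for τ = 0.25 it is 2.52.

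| Analysis | τ = 0.20 | τ = 0.25 |
|---|---|---|
| Continuous score | Φ(0.06) = 52% | Φ(0.56) = 71% |
| Split, 50% high-risk | Φ(−0.35) = 36% | Φ(0.05) = 52% |
| Split, 30% high-risk | Φ(−0.43) = 33% | Φ(−0.04) = 48% |
| Split, 20% high-risk | Φ(−0.55) = 29% | Φ(−0.19) = 42% |

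The documents use a one-sided 0.05 level. Two-sided is used here because the plan does not state a direction for the moderation. Replacing 1.96 by 1.645 at τ = 0.20 gives 65% for the score, and 49% and 46% for the split at 50% and 30% high-risk. The powers are lower with a two-sided test, but the ordering is the same. Baseline adjustment would raise all these powers and leave the efficiencies in Step 1 unchanged.

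**Step 3: how far the result depends on the assumptions.**

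- *Uniform score over 0-100, linear moderation.* The squared correlation is (1/8)² / [(1/12)(1/4)] = 0.75, a loss of 25%.
- *Bounded bell-like or skewed (beta) scores, means 30-60 and SDs 12-20, linear moderation.* The loss runs from about 31% to 71%. It is largest when few patients score above 50.
- *A true step in the effect at 50.* The split loses nothing. In simulation with 408 patients, the split had about 78% power and the linear term 48-60%, depending on the share above 50. When the truth was linear in the same simulation, the linear term had 78-80% and the split 45-57%.

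**The case against.** The strongest reply is that the analysis is exploratory, is absent from the confirmatory hypotheses and has no significance claim attached. The Protocol frames the question as one about a sub-group. A single prespecified cut that matches the baseline risk definition answers that question directly and prevents a search for a favourable cut-point. If the effect does step at 50, the planned analysis is also the more powerful one. All of this stands. It is why the split should be kept and why the point is minor. It does not explain why the score is left unused, and it does not supply the missing interaction term. The same SAP does name an arm by mediator interaction in its mediation models.

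Some stronger readings are tempting, and the documents do not support them:

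- A reader might infer that the plan discards a known fraction, such as a third to a half of the information. That needs a near-normal score, linear moderation and a share above 50 that is not extreme (about 21% to 79%). The documents give none of these.
- A reader might infer that the split alone would make a null result uninformative. At 0.20 SD per SD the continuous score itself reaches only about 52% power, so a null would be weak evidence either way.
- The Protocol's Sample size section says "To enable mediation and sub-group analyses two subgroups are required", and a reader might take the doubling as power for this moderator test, or as a fault of the split. That sentence does not mention the ÖMPSQ, and whether doubling powers an interaction is a separate sample-size question.
- ÖMPSQ risk category also appears among the candidate covariates, to be used where relevant. No harm to the treatment estimate follows from that on the evidence here.

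**Conclusion.** The point holds as a minor, cheap improvement. Moderation by ÖMPSQ is planned only through the split at 50, and the test is not stated as an interaction.

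If moderation is roughly linear and the score roughly normal, the split keeps about 64%, 58% and 49% of the information at high-risk shares of 50%, 30% and 20%. At an assumed 0.20 SD per SD, power falls from about 52% to 36%, 33% and 29%. These figures illustrate the cost under stated assumptions; they are not properties of this trial. The loss could be nearer 25% or well above 50%, and it is nil under a true threshold at 50.

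The documents offer no evidence for such a threshold in the treatment effect, and the Protocol itself calls the scale's predictive ability uncertain. That favours an analysis that can show either shape. No confirmatory hypothesis depends on the outcome.

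**What to change.** Amend the Moderator analyses paragraph in the SAP's Predictors and sub-groups section:

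- State the main moderator test as the arm × continuous ÖMPSQ interaction in the baseline-adjusted model at time points 3 and 4.
- Check linearity with a quadratic or spline term, and show the estimated effect with its 95% CI across the score, including at 50.
- Keep the prespecified above-50 versus 50-or-below analysis alongside it, expressed as an arm × category interaction with subgroup estimates and CIs.
- State that no moderation claim will be made from separate within-subgroup p-values.

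The cost is SAP wording only, since the score is already collected. The downsides are one extra exploratory analysis and lower power for the linear term if the effect truly steps at 50. The retained category contrast and the non-linearity check guard against the second.
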